[REDACTED]	[REDACTED] in [REDACTED] reaches [REDACTED] after [REDACTED] [REDACTED] (the [REDACTED] visit)	All available cumulative safety, PK, PD, immunogenicity, and efficacy data through the [REDACTED] visit in [REDACTED] the [REDACTED] visit in [REDACTED] and the [REDACTED] visit in [REDACTED]	
 
• Potential addition of up to 6 participants to Cohort 2 and/or Cohort 3 (maximum of 12 participants total in Cohorts 2 and 3)
 
• [REDACTED]
 
• [REDACTED]
 
• Inform Sponsor's decision-making regarding [REDACTED]
 

[REDACTED]	[REDACTED] dosed completes study	All available cumulative safety, PK, PD, immunogenicity, and efficacy data for all participants enrolled	Inform Sponsor's decision-making regarding [REDACTED]

Abbreviations: PD = pharmacodynamics; PK = pharmacokinetics.

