### 5.2 Data Conventions

- **Period definition:**
  - **Screening/Run-In Period:** Starts at the Screening visit until the day before first treatment, approximately Study Day -56 to -1. If a participant has an HAE attack during the Run-In period before Day 1, all signs and symptoms of the HAE attack must be resolved before dosing.
  - **Treatment & Follow-up Period:** The period from date of first dose to End of Study Date.
  - **End of Study Date:** The latest of date of Early Termination visit or as designated by “End of Study” CRF page.
  - **Treatment Period (for HAE assessments)** is defined in [Section 9.1](#); for this period the last scheduled visit for each cohort is Day 168 visit for cohort 1, Day 251 visit for cohort 2, and Day 195 visit for cohort 3. The last assessment date or last dose date can be used for participants that have not reached the end of their cohort’s treatment period.
  - **First Dose Period (for HAE assessments)** is defined as the first dose until participant’s second dose (cohorts 2 & 3) or end of treatment period.
  - **Study day:** Relative to the date of first treatment of STAR-0215: assessment date – first treatment date (+1 if assessment is after first treatment).
- **Conversion factors:**
  - 1 month = 30.4375 days
  - 1 year = 365.25 days
  - 1 week = 7 days
- **Additional rules**
  - (Absolute) Change from baseline = Value at the time point – Baseline value.
  - Relative change from baseline = [(Value at the time point – Baseline value) / Baseline value] x 100.

- % inhibition (of pharmacodynamic assessments) =  $1 - [\text{postdose rate} / \text{predose rate}] \times 100$ .
- Duration on Study = (End of Study Date – Date of First STAR-0215 treatment) +1.
- Duration of Treatment Period = (Last Treatment period assessment date – Date of First STAR-0215 treatment) +1.

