### 6.2.6 Missing, Unused, and Spurious Data

Data will be analyzed as observed. No imputation for missing data will be performed unless otherwise specified.

For binary endpoints participants who discontinue treatment will be considered as non-responders.

No other imputation of missing endpoints will be used.

For partial or missing AE start dates the following imputation will be applied:

1. If year is not missing and is after the year of first dose:
  - a. If month is missing, then month will be imputed as January.
  - b. If day is missing, then day will be imputed as the first of the month.
2. If year is not missing and is the same as the year of the first dose:
  - a. If month is missing, then impute the month as the month of the first dose date.
  - b. If day is missing, and the month is the same as the month of the first dose date, then impute day as the day of the first dose date.
  - c. If day is missing but month is after the month of first dose date, then impute day as the first day of the month.
3. If year is missing then impute the year as the year of the first dose date:
  - a. If month is missing, then impute the month as the month of the first dose date.
  - b. If day is missing, then impute the day as the day of the first dose date.
4. If the start date is completely missing, but the AE is either ongoing or the stop date is after the first dose date then impute the start date as the first dose date.
5. For any cases involving the rules above, if the AE end date is before the AE start date, then do not impute the AE start date and assume that the AE is treatment emergent for the

purpose of the analysis. Further, if the AE stop date occurs prior to the first dose date, do not impute the AE start date, and assume that the AE is not treatment emergent.

No imputations will be applied to AE stop dates.

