### 6.4.1 Change from Baseline in Monthly HAE attack rate

HAE attack rate will be expressed as the number of unique investigator-confirmed HAE attacks per month. Only unique (non-overlapping) HAE attacks will be counted; attacks are considered overlapping when a start date falls within 24 hours of an earlier attack's end date. The HAE attack rate will be calculated as:

$(\text{number of HAE attacks} / \text{duration of evaluation period in days}) * 30.4375$ ; where the duration of participants' run-in period and post-treatment follow-up periods is defined in [Section 9.1](#) and [section 5.2 \(Treatment period\)](#).

Change from baseline (Run-In period) to on treatment HAE attack rate, will be summarized by the absolute and percentage change from Baseline. Descriptive statistics (mean, median, standard deviation, Q1, Q3, minimum and maximum values) and 95% CI will be presented. The proportion of participants with a clinical response to treatment will be presented in increments as greater than or equal to 50%, 70%, and 90% reduction of HAE attacks.

A plot of individual participant's HAE attacks over time will display duration and severity by cohort. The plot will begin in the run-in phase through the last HAE assessment. The scheduled dose(s) of each cohort will be represented with dotted-lines. This plot will also be created by HAE attack location or overall cohort plot (combining participants).

HAE attacks per month (attack rate) will be presented at 4-week intervals (28 Days) from treatment start; first dose period, and 3 and 6 month intervals following last dose; and the first 3 and 6 months from Baseline (from initial dose) will also be provided. The mean monthly rate, change from baseline, and 95% CI will be presented; percent change will also be presented for monthly rates. Additional analysis of participants who have completed each interval may be performed.

Analysis of overall HAE attack rate or certain intervals, will be performed on sub-categories of HAEs: by HAE severities Mild, Moderate, Severe, and Moderate or Severe; and those that required therapy (“rescue medication”).

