#### 6.4.2 HAE Attack Incidence and Severity

The incidence and proportion of HAE attacks by worst severity (none/attack-free, mild, moderate, and severe) will be summarized.

The proportion of participants who are attack free for the entire treatment period; first dose period, and in 3 month intervals following second/last dose; and the first 3 months and 6 months from Baseline will be summarized.

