#### 6.4.5 HAE Attack Free Days

Descriptive statistics for the number of HAE attack free days will be provided for Baseline and on treatment. Attack Free Days may consider overlapping attacks to count any day on study without an attack. The proportion of HAE attack free days will also be provided, calculated as: the number of HAE attack free days / duration of evaluation period in days. In addition to overall post-treatment summary, the proportion of HAE attack free days will be presented in 3 month intervals and 6 months from first dose (for Cohort 1) and 6 months from *second dose* (for Cohorts 2 and 3). Additional analysis of participants who have completed each interval may be performed.

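### The crude attack-free proportions in SAP 6.4.2 have no rule for unfinished windows, and can be biased upward when participants are still in follow-up or withdrew after their last dose

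*SAP*

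**What the plan says.** - **Endpoint (SAP 6.4.2).** The table is to show "The proportion of participants who are attack free for the entire treatment period; first dose period, and in 3 month intervals" after the second or last dose, plus the first 3 and 6 months from Baseline. No denominator or minimum follow-up is given.
- **Period definition (SAP 5.2).** The HAE treatment period normally ends at the Day 168, 251 or 195 visit (Cohorts 1, 2, 3). However, "The last assessment date or last dose date can be used for participants that have not reached the end of their" cohort's period. The first dose period can end at the same truncated point.
- **Missing data (SAP 6.2.6).** "Data will be analyzed as observed", with one exception: "For binary endpoints participants who discontinue treatment will be considered as non-responders".
- **Analysis set (SAP 4.1.2).** One post-baseline HAE assessment is enough for entry, apart from the exclusion for important deviations.
- **Interim data (SAP 2.5, Table 5).** The added analysis takes in "All available cumulative safety, PK, PD, immunogenicity, and efficacy data for all participants enrolled", next to a separate analysis of the first 16 participants dosed, once they have completed. For one interim analysis, 2.5 mentions participants with data up to 90 days after first dose; which participants is redacted.
- **Completed intervals.** For the attack rate (6.4.1) and attack-free days (6.4.5), "Additional analysis of participants who have completed each interval may be performed". Section 6.4.2 has no such sentence.
- **Time to first attack (SAP 6.4.6).** Kaplan-Meier with censoring, after first and after last dose, with the proportion having a first attack at 28, 56, 84 and 168 days.

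**The concern.** Attack freedom over a window is known only when the window has been observed in full or an attack has already occurred. A participant followed for 8 weeks with no attack meets the SAP 5.2 definition of attack free for the entire treatment period if the period is cut at the last assessment. Shorter observation can only raise the chance of seeing no attack, so the error runs one way.

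The non-responder rule does not close the gap. A participant ongoing at a data cut has not discontinued anything. Protocol 5.3 and 5.4 separate stopping study drug from leaving the study. After the only dose (Cohort 1) or the second dose (Cohorts 2 and 3) no treatment is left to discontinue, and SAP 5.4 uses a withdrawn participant's data up to the point of discontinuation.

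At stake is how interim efficacy is read in cohorts of 4 to 12, where one or two partial windows visibly move a percentage. SAP 2.5 says that efficacy results may inform adding participants to Cohorts 2 or 3.

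**Working it through.** The documents give no attack-free figure, no on-treatment attack rate and no sample-size calculation, so there is no plan figure to reproduce. Everything below is illustration under stated assumptions.

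**1. Entire treatment period.** Assume a constant attack hazard. If p is the true attack-free probability over D days, a participant seen for d days is attack free with probability p^(d/D). Take Cohort 3 with 6 participants complete (D = 195 − 1 = 194) and 6 added participants at d = 56. The 6 + 6 split and the 56 days are assumptions; the cohort maximum of 12 is in the protocol.

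| True p | At 56 days | Crude proportion, (p + p^(56/194))/2 | Excess |
|---|---|---|---|
| 0.30 | 0.706 | 0.503 | +20 points |
| 0.50 | 0.819 | 0.659 | +16 points |
| 0.70 | 0.902 | 0.801 | +10 points |

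**2. Withdrawal after the last dose.** A Cohort 1 participant who leaves at Day 28, when the true 168-day probability is 0.50, is scored attack free with probability 0.5^(28/168) = 0.891.

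**3. Six-month window with 90-day follow-up.** Assume a constant rate r per month, so P(attack free) = exp(−r × days/30.4375). Take six participants, three seen for 6 months (182.6 days) and three for 90 days, with the partial windows kept as attack free if no attack was seen.

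| r per month | Full observation | Partial counted as success | Partial counted as failure |
|---|---|---|---|
| 0.1 | 54.9% | 64.6% | 27.4% |
| 0.2 | 30.1% | 42.7% | 15.1% |
| 0.3 | 16.5% | 28.9% | 8.3% |
| 0.5 | 5.0% | 13.9% | 2.5% |

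The excess is about 9 to 13 points. Counting every unfinished window as a failure errs the other way by more in the first two rows, so that is no remedy. For a 3-month window, 90 of 91.3 days makes almost no difference (55.4% against 54.9% at r = 0.2).

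**4. Window length against follow-up.** On SAP 5.2's conversion, 6 months is 6 × 30.4375 = 182.6 days. The final HAE visit falls 168 − 1 = 251 − 84 = 195 − 28 = 167 days after the last dose, ±7, so at most 174. No on-schedule participant completes 182.6 days after the last dose. With 6.4.6's time formula (date difference plus 1), the final visit falls at time 168 in every cohort.

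**5. Responder proportions.** SAP 6.4.1 states that "HAE attack rate will be expressed as the number of unique investigator-confirmed HAE attacks per month", divided by observed days, and then that "The proportion of participants with a clinical response to treatment will be presented in increments as greater than or equal to 50%, 70%, and 90" per cent reduction. Take 2 attacks in a 56-day run-in, baseline treated as known, and Poisson attacks after an assumed true 80% reduction. The mean is 0.4 attacks in 56 days and 0.4 × 194/56 = 1.386 in 194 days. Attacks allowed are the whole-number part of (1 − threshold) × 2 × days/56.

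| Threshold | Allowed at 56 / 194 days | P(response) at 56 days | At 194 days |
|---|---|---|---|
| ≥50% | 1 / 3 | 93.8% | 94.8% |
| ≥70% | 0 / 2 | 67.0% | 83.7% |
| ≥90% | 0 / 0 | 67.0% | 25.0% |

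With an assumed 60% reduction instead, the ≥50% figure goes from 80.9% at 56 days to 69.8% at 194 days. Direction therefore depends on threshold and effect. Only ≥90% at this low baseline behaves like attack freedom.

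**The case against.** **The SAP does not say that partial windows count as successes.** This stands. The wording in 5.2 is permissive, and it shortens the treatment period and, through it, the first dose period. It says nothing about the 3- and 6-month windows. A reader might infer that the interim proportions are inflated as a matter of rule; the text supports only that they can be. For the entire treatment period, though, no alternative handling is offered.

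**Other safeguards exist.** SAP 6.2.1 calls for a missing-data category in categorical tables, the initial 16 participants are analysed separately, all attacks are listed, and 6.4.6 already censors properly. These limit the harm. But nothing assigns an unfinished window to the missing category, and the Kaplan-Meier result would stand beside a crude proportion that may disagree with it.

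**A reader might infer that the responder proportions share the defect.** They do not in general. They sit beside a time-normalised rate, and working step 5 shows movement either way at ≥50% and ≥70%.

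**A reader might infer that the decision to add participants rests on inflated figures.** The documents do not support that. These are descriptive secondary outputs with no test and no decision threshold. Table 5 ties expansion to the first two analyses and the third to a redacted sponsor decision, and working step 1 describes the third. What remains is that 2.5 allows efficacy results to inform expansion.

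**A simple completed-window rule could misfire.** This also stands. By working step 4, a 182.6-day window after the last dose would exclude, or score as failures, participants who finished on schedule.

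**Conclusion.** The concern holds as a gap that permits a one-directional bias. SAP 6.4.2 leaves unfinished attack-free windows undefined, 5.2 and 6.2.6 allow them to be kept as attack free, and the non-responder rule misses ongoing participants and withdrawals after the last dose. The affected outputs are the entire-treatment-period proportion in cumulative data, and the 3- and 6-month proportions if partial windows stay in the denominator.

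Under constant rates, with half the cohort seen for 56 or 90 days, the excess is roughly 9 to 20 points. The split, the follow-up times and the rates are all assumptions. With few partly observed participants the bias shrinks toward zero. It is absent for completed windows and for the initial-16 analysis if all 16 have full follow-up. The responder tables need no general correction on this ground. The plan should be changed, because the remedy uses a method already in it.

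**What to change.** 1. In SAP 6.4.2, report the attack-free probability as the Kaplan-Meier estimate with its 95% CI, after first dose and after last dose, at fixed days within scheduled follow-up. Days 84 and 168 match 6.4.6. Do not use 182.6 days. Day 168 is the last scheduled day after the last dose and the visit window is ±7, so print the number at risk.
2. If a crude proportion is also shown, limit the denominator to participants whose window start lies at least the window length before the data cut-off. This depends on the calendar and not on outcome. Keeping early attacks but dropping those attack free so far would bias the result downward.
3. State window lengths in days, and count on-schedule completion of the cohort's final visit (Day 168, 251 or 195) as completing the window.
4. State how study withdrawals before that visit are classified, including those after the last dose.

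The cost is SAP wording and one table, with no new data. Interim percentages will be lower or rest on fewer participants. Kaplan-Meier also assumes that censored participants have the same later attack risk as those still observed, which is less secure for withdrawals than for participants censored by a data cut.

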#### 6.4.3 HAE Attack Duration

The duration of each participant’s longest HAE attack will be presented with descriptive statistics and for the following categories: shorter than 12 hours, 12 to 24 hours, 24 to 48 hours, and longer than 48 hours.

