9.6. Efficacy Analysis

Unless otherwise specified, all analyses of HAE attack data will be presented similarly during the Run-In and treatment periods using the Efficacy Analysis Set. Data will be summarized for all investigator-confirmed HAE attacks.

The frequency and duration of HAE attacks will be presented with descriptive statistics overall and by participant. The following categories will be presented for attack duration: shorter than 12 hours, 12 to 24 hours, 24 to 48 hours, and longer than 48 hours.

Attack severity categorized as Mild, Moderate, or Severe will be presented overall and by participant.

The number and type of on-demand therapies used to treat HAE attacks will be summarized.

The proportion of HAE attack-free participants during the treatment period will be summarized.

The time normalized number of investigator-confirmed HAE attacks per month (attack rate) will be presented at 4-week intervals and at the end of the study. The mean monthly rate and 95% confidence interval will be presented.

To assess HAE attacks within a participant, the actual and percentage change from baseline (Run-In period) in monthly attack rate with respect to on-treatment attack rate will be calculated. The mean change and 95% confidence interval will be presented.

The proportion of participants with a clinical response to treatment will be presented in increments as greater than or equal to 40%, 50%, 60%, 70%, 80%, 90%, and 100% reduction of HAE attacks relative to baseline will be presented.

Time to first HAE attack after first and last dose of STAR-0215 will be presented using Kaplan-Meier estimates.

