#### 3.2 Secondary Endpoints - Efficacy

- Change from baseline in monthly HAE attack rate, overall and per month.
  - 50%, 70%, and 90% overall reduction of HAE attacks
  - Investigator assessed HAE Attack definition is given in Protocol section 7.12.1:

To be considered an HAE attack, the Investigator must confirm that the event has signs or symptoms consistent with an HAE attack that meet at least 1 of the following criteria: Peripheral angioedema, Abdominal angioedema, or Laryngeal angioedema.

Prodromal symptoms or participant-reported use of on-demand HAE attack treatment alone are not sufficient to define an event as an HAE attack.

Each HAE attack must be unique. To be distinct from the previous attack, the new symptoms must occur at least 24 hours after resolution of the prior attack's symptoms.

The HAE attack resolution is defined as the participant no longer having symptoms of the HAE attack. The HAE attack severity will be graded by the Investigator.
- Proportion of participants who are HAE attack free
- Incidence of at least one HAE attack by maximum severity (mild, moderate, and severe), including participants without any attacks.
- Duration of HAE attack (shorter than 12 hours, 12 to 24 hours, 24 to 48 hours, and longer than 48 hours).
- The number of HAE attacks requiring on-demand therapy.
- Time to first HAE attack after first and last dosing, censored to End of Study visit.
- HAE attack free days, from treatment start until End of Study.

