#### 6.2.2 Definition of Baseline

For the analysis of HAE attacks, the Run-In Period will be considered as Baseline for rate, incidence or duration of HAE attacks.

For all other endpoints baseline is defined as the last non-missing assessment prior to the first dose of STAR-0215.

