## 6.4 Efficacy Evaluation

All analyses of HAE attack data will be presented using the Efficacy Analysis Set. Both Run-In and Post-Treatment period will be displayed where applicable.

All HAE attacks that occurred on study will be listed for both Run-In and Treatment periods.

A summary of Run-In period HAE attack assessments will include Location of HAE attacks (Abdominal, Laryngeal, Peripheral); the baseline (Run-In period) values of: HAE attack rate, HAE attacks by worst severity (none/attack-free, mild, moderate, and severe), duration of each participants longest HAE attack, number and proportion of HAE attacks requiring on-demand therapy, and HAE Attack Free Days. This summary will be repeated for the first dose period.

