#### 6.4.4 HAE Attack Requiring Therapy

The number of HAE attacks and the proportion of participants requiring on-demand therapy at baseline and during the treatment period will be summarized. The type of on-demand therapies used to treat HAE attacks will also be summarized.

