## 7 CHANGES TO [REDACTED]

Protocol text related to Section 2.5 [REDACTED] was revised: due to fast enrollment each [REDACTED] will include additional participants and available [REDACTED] data.

Otherwise, there have been no changes between the protocol-defined statistical analyses and those presented in this statistical plan.

A [REDACTED] will take place when the first 16 participants dosed have completed treatment follow-up. Separate analyses will be performed for the “initial 16 participants’ and for all cumulative data at the time of the data cut-off.

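### Attack duration is summarised only through each participant's longest attack, which depends on the number of attacks and so can show a duration shift when there is none

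*SAP*

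**What the plan says.** The protocol's endpoint table (Section 3) lists attack duration in four categories, and SAP 3.2 repeats it: "Duration of HAE attack (shorter than 12 hours, 12 to 24 hours, 24 to 48 hours, and longer than 48 hours". Protocol 9.6 says how it is to be analysed: "The frequency and duration of HAE attacks will be presented with descriptive statistics overall and by participant". The same section bases the efficacy summaries on all investigator-confirmed attacks.

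SAP 6.4.3 plans something else. There each participant's "longest HAE attack will be presented with descriptive statistics and for the following categories", followed by the same four bands. SAP 6.4 lists the "duration of each participants longest HAE attack" among the run-in results and adds: "This summary will be repeated for the first dose period". SAP 6.2.2 makes the run-in the comparator: "the Run-In Period will be considered as Baseline for rate, incidence or duration of HAE attacks".

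SAP 3.2 does state a per-participant maximum for severity, but not for duration. Apart from the revised timing and content of the redacted item in its Section 2.5, SAP Section 7 says that "there have been no changes between the protocol-defined statistical analyses and those presented in this statistical plan".

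**The concern.** A participant's longest attack is a maximum, and a maximum grows with the number of attacks it is taken over. That number differs between the periods being compared for two reasons unrelated to how long an attack lasts. The treatment window is several times the run-in, and attack frequency is what the drug is meant to change. Eligibility also guarantees at least 2 attacks in the run-in, with no counterpart on treatment. The table can therefore show longer or shorter attacks on treatment when individual attacks are unchanged. Cohorts with the same frequency effect can differ because their windows differ.

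SAP 6.4.3 also has no category for a participant without attacks, although SAP 6.4.2 has one for severity. Such a participant has no longest attack, so the on-treatment table covers a selected subset without saying so.

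**Working it through.** The documents give no figure for duration, so there is nothing of the plan's own to reproduce.

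**Inputs from the documents.** Run-in of at least 56 days (Protocol 4.5), with at least 2 attacks (inclusion criterion 9). Treatment period for HAE assessments to Day 168, 251 and 195 in Cohorts 1, 2 and 3 (SAP 5.2). One month is 30.4375 days (SAP 5.2). The windows are 168/56 = 3.0, 251/56 = 4.5 and 195/56 = 3.5 times a 56-day run-in.

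**Assumptions, not in the documents.** Independent lognormal durations, identical before and after dosing (median 24 h with log-SD 0.5 or 0.8; median 36 h with log-SD 0.6). Poisson attack counts at 1.5, 2 or 3 per month in run-in. Rate reductions of 0 to 95%.

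**Step 1: fixed number of attacks.** If one attack has distribution F, then P(longest ≤ x) = F(x)^n. For median m and log-SD s, the median longest attack is m·exp(s·Φ⁻¹(0.5^(1/n))). With m = 24 h and s = 0.8, F(48) = Φ(ln 2/0.8) = 0.807:

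| n | Median longest attack (h) | P(longest > 48 h) |
|---|---|---|
| 1 | 24.0 | 0.19 |
| 2 | 37.1 | 0.35 |
| 4 | 53.3 | 0.58 |
| 6 | 64.3 | 0.72 |
| 12 | 85.5 | 0.92 |

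**Step 2: realistic counts.** F(x)^n was averaged over a Poisson count, conditioned on at least 2 attacks in run-in (eligibility) and at least 1 on treatment (a longest attack needs an attack). At 2 per month the unconditioned run-in mean is 2 × 56/30.4375 = 3.68. In Cohort 1 the treatment mean is 2 × 168/30.4375 = 11.04 times (1 − reduction). For median 24 h and log-SD 0.8:

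| Period | Rate reduction | Median longest attack (h) | P(longest > 48 h) |
|---|---|---|---|
| Run-in | – | 52.2 | 0.56 |
| Cohort 1 | 0% | 81.7 | 0.88 |
| Cohort 1 | 50% | 60.3 | 0.66 |
| Cohort 1 | 70% | 47.3 | 0.49 |
| Cohort 1 | 90% | 31.4 | 0.29 |
| Cohort 2 | 90% | 35.4 | 0.34 |
| Cohort 3 | 90% | 32.7 | 0.30 |

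The last three rows differ only through window length.

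**Step 3: where the direction changes.** Expected counts match a 56-day run-in when the reduction is 1 − 56/168 = 67%, 1 − 56/251 = 78% or 1 − 56/195 = 71%. Below that the longest attack tends to look longer on treatment, and above it shorter. Because eligibility lifts the run-in count, the medians of Step 2 cross slightly lower. Solving for equal medians at 2 per month gives about 63%, 75% and 68%.

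**Step 4: range.** Over all the assumptions, in Cohort 1, the median longest attack is 36.9 to 72.5 h at run-in, 47.9 to 101.6 h at 0% reduction and 27.3 to 48.2 h at 90%.

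**Step 5: participants left out.** At 2 per month and a 90% reduction, the chance of no attack is exp(−0.2 × 168/30.4375) = 0.33 in Cohort 1, and likewise 0.19 in Cohort 2 and 0.28 in Cohort 3.

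**Step 6: the Protocol 9.6 summary under the same assumptions.** Taken over all attacks (median 24 h, log-SD 0.8), the median is 24 h and P(> 48 h) is 0.19 in both periods, whatever the count or window.

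The first-dose-period table does not remove the problem. Its windows are about 168, 83 and 27 days against 56.

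**The case against.** Several points on the other side stand. Duration is secondary, SAP 6.4.3 plans no test, confidence interval or change from baseline for it, and SAP 6.2.1 rules out formal hypothesis testing. Every attack is listed (SAP 6.4) and plotted with its duration (SAP 6.4.1), so the data stay visible. The proportion of attack-free days in SAP 6.4.5 is adjusted for window length and includes attack-free participants. It mixes frequency with duration, however, and the listing and plot are not a summary. None of these gives a duration result free of attack count.

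The independence assumption matters too. If attacks within a participant have similar durations, the dependence on n shrinks.

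One value per participant also has a merit. With 4 to 12 participants per cohort, a frequent attacker can dominate pooled percentages. And a per-attack table likewise contains nothing from attack-free participants. Both are reasons to report by participant as well as overall and to state who is missing. They do not justify using the maximum. The protocol's by-participant wording could cover a per-participant statistic, but the overall summary is still absent.

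A reader might infer that worst severity (SAP 6.4.2) and the statement that "the proportion of participants requiring on-demand therapy at baseline and during the treatment period will be summarized" (SAP 6.4.4) fail in the same way. The documents do not support carrying the point that far. SAP 6.4.1 plans attack rates by severity and for attacks needing therapy, SAP 6.4 plans the proportion of attacks treated on demand for the run-in and first dose period, and maximum severity is the endpoint SAP 3.2 declares.

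**Conclusion.** The point holds for duration. The only planned summary is a per-participant maximum. This departs from Protocol 9.6 and from SAP 3.2, is not declared in Section 7, and is compared across windows of at least 56 days against 168, 251 or 195 days. The dependence on attack count follows for independent attacks with any non-degenerate duration distribution. The hours quoted rest on assumed durations and rates and on independence between attacks.

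A reader might infer that any drug that lowers attack frequency will appear to shorten attacks. That is not so. In the Cohort 1 example a 50% rate reduction moves the median longest attack up, from 52 h to 60 h, and the artefact largely cancels near 67%, 78% and 71% in Cohorts 1, 2 and 3. Apparent shortening needs a larger reduction.

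With no test planned, the harm is a misleading descriptive table, not a type I error. It should be corrected but does not threaten the primary safety objective.

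**What to change.** In SAP 6.4.3, add the Protocol 9.6 analysis as the main duration summary. Place every unique investigator-confirmed attack in the four categories, with descriptive statistics overall and by participant (for example each participant's mean or median duration, so that a frequent attacker does not dominate), for run-in and for treatment. State beside the table how many participants are attack-free and so not included. Keep the longest attack as supportive only, here and in SAP 6.4. Declare the choice in Section 7. The SAP's modification history shows that an interim analysis has already been run in this open-label study, so a declared addition is better than a silent rewrite.

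The cost is SAP wording and one reprogrammed table. Time of onset and duration of each attack are already collected (Protocol 7.12).
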